5.2 Randomization and blinding

The participants will be randomized 1:1 to receive double-blind single-dummy monotherapy with placebo or ZYP using the permuted block randomization method. The randomization will be stratified by the age (35-37, 38-39 and 40-42) by following the Human Fertilisation and Embryology Authority (11). The web-based Interactive Response Technology system is managed by independent statisticians, guiding drug dispensing.

Patients, investigators and clinical staff performing this trial will be blinded to treatment allocation. The package, appearance and odor are the same in the placebo and ZYP. The allocation and detailed information of randomization will be kept by the independent statisticians managing the Interactive Response Technology system. Blinding will be maintained until the completion of the analysis. Unblinding will be allowed in case of a medical emergency. The cause and time of unblinding will be recorded in detail and signed by the treating physicians.

When all live birth information is retrieved, the computer system will disclose the allocation.

5.3 Intervention of IVF/ICSI and study drug

5.3.1 Controlled Ovarian Hyperstimulation (COH)

Two COH protocols will be applied.

1) GnRH-a long protocol: All subjects in two groups will undergo COH after down-regulation with long-acting or short-acting GnRH-a in midluteal phase. Hormone levels, including follicle-stimulating hormone (FSH), luteinizing hormone (LH) level and estradiol (E₂) will be measured on the gonadotropin (Gn) initiation day. Follicular development (diameter and counts) and endometrial thickness will also be evaluated by means of transvaginal ultrasonography. COH will be initiated when the serum LH < 5 IU/L and E₂ < 50 ng/ml or endometrial thickness < 5 mm. The initiation dose and total Gn dose will be adjusted according to a combined consideration of age, weight, basal hormone levels, antral follicular count (AFC) and

previous cycle response.

2) GnRH-ant protocol: Initiation will be conducted on day 2 to day 4 of menstrual cycle. Hormone levels, including FSH, LH and E₂ levels will be measured on the Gn initiation day. Follicular development (diameter and counts) and endometrial thickness will also be evaluated by means of transvaginal ultrasonography. The initiation dose and total Gn dose will be adjusted according to a combined consideration of age, weight, basal hormone levels, AFC and previous cycle response.

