6.3 Gn initiation visit

During the Gn initiation visit, the following procedures will be completed.

- (1) Adverse events and treatment (if necessary).
- (2) Medication on Gn initiation, including type, name, initiation dose.
- (3) Serum hormone levels, including E₂, FSH, LH, and P₄.
- (4) Dispensing and return information.

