6.7 Delivery visit

When the participant is preparing to deliver, the investigator will collect the delivery information and infant information according to the form designed for this visit. The delivery information mainly includes the delivery mode and pregnancy complications. The neonate information mainly includes gender, birth weight and length, birth

defects, admission to newborn intense care unit within 1 month and stillbirth.

7. Physical examination

A physical examination will be conducted on all participants by the corresponding investigator. The parameters include height, weight and they will be recorded to the nearest 0.1 cm, 0.1 kg. Height and weight will be measured without shoes, and patients will be dressed in light clothing.

8. Transvaginal ultrasound scan

An ultrasound scan with a transvaginal probe will be carried out. Uterine dimension, endometrial thickness and type, bilateral ovarian dimension, and follicle number will be measured through the ultrasound scan. The uterine size will be determined at the widest diameter. The investigator will determine endometrial types. Endometrial thickness is the largest anterior-posterior measurement of the endometrium in the sagittal plane. Ovarian dimension is measured by analysis of the largest plane of the ovary in two dimensions. In addition, antral follicle count (AFC) will be recorded.

9. Laboratory tests

Hormone and pregnancy tests will be performed at the local laboratories. In addition, blood work will be performed on screening visit, Gn initiation visit, hCG trigger day, and 2 weeks after ET. The blood sample (5 ml) will be collected with an anticoagulant tube and stored at -80°C for further analysis.

10. Outcome measures

The live birth rate is the primary outcome. The secondary outcomes will include counts and rates of oocytes/embryos (oocytes retrieved, 2 pro-nuclei zygotes, cleavage zygotes, available embryos, high-quality embryos), pregnancy outcomes (rates of biochemical pregnancy, implantation, clinical pregnancy and miscarriage),

incidences of maternal, fetal and neonatal complications, neonate information (newborn birthweight and length, congenital malformation) (14).

Live birth is defined as delivery of any viable infants after 28 weeks of gestation.

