The planned duration of recruitment will be 24 months with 12 centers. The enrollment target of our clinical trials is 1466 randomized participants. The number of participants taken in each center will be allocated according to the actual situation. The treatment period may need about 3 months and another 9 months to trace the pregnancy outcome. In short, a total of 36 months will be required to complete this trial, from initial recruitment to pregnancy outcome period.

12. Statistical analysis plan

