12.2 Sample size estimation

In our previous clinical research, the live birth rate was 0.42 per embryo transfer in ZYP treated group and 0.33 per embryo transfer in placebo control group among AMA women. By assuming the same live birth rates, a sample size of 454 women in each group can provide a power of 80% at a significance level of 0.05. According to previous study, the dropout rate before ET was 15% and the cycle cancellation rate was 23% in AMA women. For this trial, a total rate of 38% (dropout and cancellation) is considered in the sample size calculation. Therefore, a total of 1466 participants

will be recruited in this study, 733 participants in each group.

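### The oestradiol limit for starting gonadotropin in the long protocol is written in ng/ml, so over any plausible range every patient meets it (minor unit error in an operative rule)

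*Combined protocol and SAP*

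**What the plan says.** Section 5.3.1 describes the long protocol as stimulation after pituitary down-regulation: "All subjects in two groups will undergo COH after down-regulation with long-acting or short-acting GnRH-a in midluteal phase". LH and oestradiol are assessed on the day gonadotropin is due to start ("estradiol (E₂) will be measured on the gonadotropin (Gn) initiation day"), and endometrial thickness is evaluated by ultrasound. The start rule follows: "COH will be initiated when the serum LH < 5 IU/L and E₂ < 50 ng/ml or endometrial thickness < 5 mm". It has three criteria, joined by *and* and *or* without brackets. No such rule is given for the antagonist protocol.

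No other place in the document gives an oestradiol unit or limit. The list for the gonadotropin initiation visit (section 6.3) reads only "Serum hormone levels, including E₂, FSH, LH, and P₄". Oestradiol is also named in sections 5.3.2, 5.3.3, 6.2, 13.1 (Table 7) and 14, each time without a unit or threshold. Section 9 says "Hormone and pregnancy tests will be performed at the local laboratories" and states no common reporting unit. Section 11 says "The planned duration of recruitment will be 24 months with 12 centers".

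**The concern.** The oestradiol criterion is there to show that the ovary is suppressed before stimulation begins. A ceiling that lies far above any value a patient could have does not do that. Everyone passes, and the decision falls to the other two criteria.

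This is a decision threshold in a treatment rule, not a slip in background text. Section 5.1 promises standardised stimulation protocols, the hormone assays are local, and this line is the only statement of the limit in the documents. A centre that follows it literally and a centre that silently reads pg/ml could handle the same patient differently, and the text would not show which was right.

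**Working it through.** **Plan's own figure.** The limit of 50 ng/ml is a stated threshold without a derivation, so there is no calculation to reproduce. The check is a unit conversion followed by a truth table.

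**Inputs.** From section 5.3.1: LH limit 5 IU/L, oestradiol limit 50 ng/ml, endometrial limit 5 mm. Assumed, because the documents do not give them: serum oestradiol on the start day between 5 and 10,000 pg/ml (deliberately wide), and a molar mass of oestradiol of 272.38 g/mol.

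**Step 1: convert the limit.** 50 ng/ml × 1,000 = 50,000 pg/ml.

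**Step 2: compare with the assumed range** (value ÷ 50,000).
- 5 pg/ml: 0.01%
- 120 pg/ml: 0.24%
- 1,000 pg/ml: 2%
- 10,000 pg/ml: 20%

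All are below 100%, so the criterion is always true within the range.

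**Step 3: what the rule becomes.** There are two possible groupings.
- A: (LH and oestradiol) or endometrium. With oestradiol always true, this reduces to LH < 5 IU/L or endometrium < 5 mm.
- B: LH and (oestradiol or endometrium). This reduces to LH < 5 IU/L alone, so the endometrial limit becomes redundant too.

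**Step 4: where the unit changes the decision.** In the table, 1 means criterion met or stimulation started. The oestradiol column uses the intended limit, taken here as 50 pg/ml. *Written* means with oestradiol always true.

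| LH < 5 | E₂ below intended limit | Endometrium < 5 mm | A intended | A written | B intended | B written |
|---|---|---|---|---|---|---|
| 0 | 0 | 0 | 0 | 0 | 0 | 0 |
| 0 | 0 | 1 | 1 | 1 | 0 | 0 |
| 0 | 1 | 0 | 0 | 0 | 0 | 0 |
| 0 | 1 | 1 | 1 | 1 | 0 | 0 |
| 1 | 0 | 0 | **0** | **1** | **0** | **1** |
| 1 | 0 | 1 | 1 | 1 | 1 | 1 |
| 1 | 1 | 0 | 1 | 1 | 1 | 1 |
| 1 | 1 | 1 | 1 | 1 | 1 | 1 |

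Only one row differs, and it is the same row under both groupings: LH met, oestradiol not met, endometrium not met. Separately, A and B disagree with each other when LH is 5 IU/L or more and the endometrium is below 5 mm, whatever the unit.

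**Step 5: an example.** Take LH 3 IU/L, oestradiol 120 pg/ml (0.12 ng/ml) and endometrium 7 mm. As written, she starts. With a limit of 50 pg/ml she is held back, at 120/50 = 2.4 times the limit.

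**Step 6: candidate units.**
- 50 pg/ml = 50 ng/L = 50 × 1,000/272.38 = 183.6 pmol/L
- 50 pmol/L = 50 × 272.38/1,000 = 13.6 pg/ml
- 50 ng/dl = 500 pg/ml

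The example patient is held back under the first two lines but would start under the third.

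**Step 7: side check on sample size.** Section 12.2 uses "the live birth rate was 0.42 per embryo transfer in ZYP treated group and 0.33 per embryo transfer in placebo control group" and concludes that "a sample size of 454 women in each group can provide a power of 80% at a significance level of 0.05". With pooled variance under the null (mean rate 0.375):

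n = [1.960 × √(2 × 0.375 × 0.625) + 0.8416 × √(0.42 × 0.58 + 0.33 × 0.67)]² / 0.09² = (1.3419 + 0.5737)² / 0.0081 ≈ 453.0, rounded up to 454 per group.

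Then 454/(1 − 0.38) = 732.3, rounded up to 733 per group, or 1466 in total. The plan's figures are reproduced, and the oestradiol limit enters none of them.

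**The case against.** The strongest reply is that this is one wrong letter with no shown consequence. Clinicians who run long protocols probably read the limit as pg/ml. The rule is identical in both arms, allocation is blinded, and only long-protocol patients are concerned. All of that stands, and it is why the point is minor. It limits the consequence but does not make the written threshold right.

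Three further objections also stand in part.
- The text was machine-read from a PDF, so a misread of n for p cannot be fully excluded. Nothing in the sentence points to one; its other units (IU/L, mm) read cleanly.
- Calling the criterion ineffective rests on an oestradiol range that the documents do not give. The range used is stated and very wide, but it remains an assumption.
- The documents reviewed may not be all that centres hold. A site manual or eCRF check could carry the right unit.

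A reader might also infer that the correction makes oestradiol a strict requirement for starting. It does not under grouping A, where an endometrium below 5 mm allows a start at any oestradiol level even after the unit is corrected. Nor does the example come out the same whichever unit was meant: with 50 ng/dl (500 pg/ml) the woman at 120 pg/ml would start, just as under the written text.

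**Conclusion.** Wrong as written, and minor. The written limit is 1,000 times 50 pg/ml. On the assumption that oestradiol on the start day lies between 5 and 10,000 pg/ml, every patient meets it and it cannot confirm down-regulation. The LH criterion still operates, alone or alongside the endometrial one depending on the grouping. The unit alters the decision only when LH is below 5 IU/L, oestradiol is at or above the intended limit and the endometrium is 5 mm or more. The documents give no oestradiol distribution, so the share of patients in that position cannot be stated. That pg/ml was intended is an inference.

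A reader might go further and infer that unsuppressed women were in fact started, or that the comparison of live birth rates is weakened. The documents support neither. They do not show that any centre applied ng/ml, and the limit plays no part in the sample size, the power or the primary intention-to-treat test. A rule common to both blinded arms gives no route to bias, and no effect on the per-protocol set is shown.

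**What to change.** In section 5.3.1, correct the oestradiol unit, probably to 50 pg/ml (equal to 50 ng/L, about 184 pmol/L), after the sponsor confirms what was intended. Giving the limit in both mass and molar units would help, since the assays are local.

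In the same edit, bracket the three criteria. The sponsor should say whether the rule is [LH < 5 IU/L and E₂ < 50 pg/ml] or endometrium < 5 mm, or LH < 5 IU/L and [E₂ < 50 pg/ml or endometrium < 5 mm]. That settles how a woman with LH of 5 IU/L or more and an endometrium below 5 mm is handled, a question the unit correction alone leaves open.

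The cost is a one-line protocol correction and a short note to the 12 centres. No test is added, because LH, oestradiol and endometrial thickness are already assessed that day. No sample size or analysis text changes.

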5.3.2 Ovulation monitoring

The mean diameter of all follicles and endometrial thickness will be monitored by means of ultrasonography, along with testing of serum hormonal levels, including FSH, LH, E₂ and progesterone (P₄) on the day 5 to day 6 after Gn initiation.

5.3.3 Oocyte retrieval and embryo transfer

When the diameter and counts of follicles meet the criteria (two leading follicles \geq 18 mm; or \geq 3 follicles \geq 17 mm; or \geq 4 follicles \geq 16 mm), ovulation will be triggered by injecting human chorionic gonadotropin (HCG). Testing of serum FSH, LH, E₂ and P₄ levels will be conducted on HCG injection day. Oocyte collection will be performed 36 hours later. Luteal support will be started on oocyte retrieval day. Fertilization will be achieved by conventional IVF or ICSI with the husband's semen. On day 3 to day 5 after oocyte retrieval, one to three embryos will be transferred.

High-quality embryos is defined according to Istanbul consensus and Gardner criteria (12, 13).

Day 2	4 cells, cell fragments <10%, no multi-nucleus
Day 3	8 cells, cell fragments <10%, no multi-nucleus
Day 5	stage 4 blastocyst, grade A inner cell mass, trophectoderm at grade A

5.4 Intervention of study drug

Eligible subjects will be allocated to receive ZYP or the placebo 3 times daily, 5 g

each time on down-regulation day (GnRH-a long protocol) or day 19 to day 23 of previous menstrual cycle (GnRH-ant protocol). Study drug will be suspended during the 1st day to the 4th day of menstrual cycle. Continuation of the study intervention will be determined by the serum β -HCG pregnancy test carried out two weeks after embryo transfer. Intervention of study drug will be stopped if the pregnancy test is negative. For patients with positive results on the pregnancy test, the study medicine will be given until a confirmed clinical pregnancy (five weeks after ET).

5.4.1 Zishen Yutai Pill

The manufacture of ZYP complies with the relevant requirements of law of China's Drug Administration and Good Manufacturing Practice (GMP), with approval from the China National Medical Products Administration (Permit No.Z44020008).

Table 5. Herbal drugs used in Zishen Yutai Pill (ZYP) and the origins and medicinal parts

Herbal drugs	Origin of natural medicine
Cuscutae Semen	Ripe dried seed of Cuscuta Chinensis Lam.
Ginseng Radix et Rhizoma	Dried root and rhizome of Panax ginseng C. A. Mey.
Dipsaci Radix	Dried root of Dipsacus asper Wall. ex DC.
Taxilli Herba	Dried leafy stem and branch of Taxillus chinensis (DC.) Danser
Eucommiae Cortex	Dried bark of Eucommia ulmoides Oliv.
Morindae Officinalis Radix	Dried root of Marinda officinalis How
Cervi Cornu Degelatinatum	Residue after water extraction of ossified antler of Cervus nippon Temminck
Codonopsis Radix	Dried root of Codonopsis pilosula (Franch.) Nannf.
Atractylodis Macrocephalae Rhizoma	Dried rhizome of Atractylodes macrocephala Koidz.
Asini Corii Colla	Solid glue prepared by stewing and concentrating from the hide of Equus asinus L.
Lycii Fructus	Dried ripe fruit of Lycium barbarum L.
Rehmanniae Radix	Steamed and dried root of Rehmannia glutinosa (Gaertn.) DC.
Praeparata	
Polygoni Multiflori Radix	Steamed and dried root of Polygonum multiflorum Thunb.
Praeparata	
Artemisiae Argyi Folium	Dried leaf of Artemisia argyi Lévl. et Vant.
Amomi Fructus	Dried fruit of Amomum villosum Lour.

5.4.2 Composition and manufacturing process of the placebo

- 1) Composition: Pregelatinized starch, microcrystalline cellulose, black iron oxide, refined honey, dextrin.
- 2) Manufacturing process: Pregelatinized starch, microcrystalline cellulose, and black iron oxide are mixed, crushed, and sieved. The refined honey is added to the mixed powder to make the wet pill with the required size. After drying, it is coated with a mixture of black iron oxide and talc powder, 3% dextrin solution, 75% ethanol solution, and refined honey. Finally, eligible pills are polished using Chinese insect wax, selected, and packaged.

5.4.3 Adherence of study drug

Patients' adherence of study drug will be assessed. An actual dosage above 80% of required drug dosage will be considered consistent with protocol requirements.

In order to record and improve the adherence of study drug, a diary card will be used. The diary card includes information of participants, study drug dosage, date of drug administered. In addition, each participant will be assigned a clinical research coordinator to assure the adherence of study drug and carry out follow-up.

5.4.4 Package and label of study drug

Both the ZYP and the placebo will be provided in the same label and appearance (written in Chinese).

Drug No.:

The Application of Zishen Yutai Pill in Aged Women Undergoing IVF-ET (Clinical Use Only) Dosage of one week

【Action and Use】 Tonify *Kidney* and *Spleen*, invigorates *Qi* that nourishes *Blood*, placate the fetus and strengthens the body. Used in pregnancy loss due to deficiency of *Kidney* and *Spleen*, debility of *Chong* and *Ren* (treatment and prevention of threatened miscarriage and spontaneous miscarriage).

【Package】 5 g/package.

【Dosage and Administration】 Administered orally with honey water or dilute salt water. 5 g (1 package) each time, tid.

【Intervention period】 11 weeks.

【Storage Condition】 Please keep in seal and away from moister.

【Caution】 Please keep the remaining drug and the package until the end of clinical trial. Stored away from children.

Manufactured by Guangzhou Baiyunshan Zhongyi Pharmaceutical Co. Ltd.

Expired Date: ** Batch No.: **

6. Study procedures and visits

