6.4 ET visit

During the ET visit, the following procedures will be completed.

- (1) Adverse events and treatment (if necessary).
- (2) Summary of COH including type, name and total amount.
- (3) B-mode ultrasound and basal serum hormonal level.

- (4) Information about semen collection, embryo development, embryo transfer information.
- (5) Information about the medicines used in luteal phase support, including name, dose, duration, and total amount.
- (6) Dispensing and return information.

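### The drug label's fixed 11 weeks and keep-leftovers line do not agree with section 5.4 or the recorded drug returns, and 5.4 states no end of dosing for cancelled cycles

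*Combined protocol and SAP*

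**What the plan says.** **Label (section 5.4.4).** Both arms carry the same label. Each labelled pack is a "Dosage of one week", taken as "5 g (1 package) each time, tid", with "Intervention period】 11 weeks" printed without any condition. The caution line reads "Please keep the remaining drug and the package until the end of clinical trial".

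**Dosing (section 5.4).** "Study drug will be suspended during the 1st day to the 4th day of menstrual cycle". Then: "Continuation of the study intervention will be determined by the serum β -HCG pregnancy test carried out two weeks after embryo transfer". A negative test ends dosing. After a positive test, drug goes on until the clinical pregnancy check five weeks after transfer.

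**Drug accounting (section 6).** Screening (6.2) lists dispensing only. The gonadotropin-start and transfer visits (6.3, 6.4) each list "Dispensing and return information". The visit two weeks after transfer (6.5) records both as well, and the visit at five weeks (6.6) records returns only.

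**Adherence (sections 5.4.3 and 12.3).** More than 80% of the required dosage counts as compliant, and a diary card records intake. The per-protocol set drops women below 80%, along with cancelled cycles and major deviations.

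**Timeline (section 11).** "The treatment period may need about 3 months".

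**The concern.** The label is the written dosing instruction that stays with the woman. If it differs from section 5.4 on how long to dose, whether to pause and when to stop, then women who follow the label and women who follow the protocol can have different exposure. If it also tells them to hold on to leftover drug, fewer packages may come back to be counted. The diary is self-reported, and returned packages are the only other record of intake that the plan describes.

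Separately, a woman whose cycle is cancelled before transfer never reaches either event that ends dosing in 5.4. What is at stake is consistency of exposure, drug accountability and the adherence criterion for the per-protocol set.

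**Working it through.** **Inputs.** Label: 11 weeks, three packages a day (5.4.4). End of dosing: 2 or 5 weeks after transfer; pause: cycle days 1 to 4 (5.4). Cancellation 23%, dropout before transfer 15%, 1,466 women (12.2). The documents do not give the time from first dose to transfer. Call it T days.

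**1. Can the label's 11 weeks be reproduced?**
- Label: 11 × 7 = 77 days; 77 × 3 = 231 packages.
- Section 5.4, calendar length: T + 35 if the test is positive, T + 14 if negative.
- The difference is 35 − 14 = 21 days whatever T is.
- 77 days matches the positive course only if T = 77 − 35 = 42, and the negative course only if T = 77 − 14 = 63. It cannot match both.

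With T unknown, 11 weeks cannot be derived from the documents. Over an assumed range of 25 to 49 days:

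| T (assumed) | Positive test, days (weeks) | Negative test, days (weeks) |
|---|---|---|
| 25 | 60 (8.6) | 39 (5.6) |
| 28 | 63 (9.0) | 42 (6.0) |
| 35 | 70 (10.0) | 49 (7.0) |
| 42 | 77 (11.0) | 56 (8.0) |
| 49 | 84 (12.0) | 63 (9.0) |

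In this range the negative-test course is always shorter than 11 weeks.

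**2. The pause.** Taking 77 days as the full course with one four-day pause leaves 77 − 4 = 73 dosing days, or 73 × 3 = 219 packages: 219/231 = 94.8% of what the label's figures give. The pause therefore matters much less than the 21-day gap.

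**3. Leftover drug.** The label says to keep it to the end of the trial. Section 6 records returns at visits 2, 3, 4 and 5. Follow-up runs on to delivery by web or telephone (6.1), and section 11 allows a further 9 months for it. Read literally, the end of the trial falls after every visit at which drug could be handed back.

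**4. No transfer.** Both end points in 5.4 are timed from transfer. Cancelled cycles: 0.23 × 1,466 = 337.

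**5. Link to the 80% rule.** Section 5.4.3 does not quantify the required dosage. To show why the course length must be settled, suppose it were taken as the label's 77 days. A woman who stopped as 5.4 directs after a negative test, with one pause, would score (T + 14 − 4)/77. That is 35/77 = 45.5% at T = 25 and 59/77 = 76.6% at T = 49, below 80% throughout despite full compliance. This is conditional: the plan does not say that 77 days is the denominator.

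**The case against.** The case on the other side is that the label can be read so that little conflicts. Much of that case stands, and it rules out several stronger readings.

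- *That the label orders continuous dosing.* A reader might infer this, but the label is silent on pauses.
- *That every woman is given an 11-week course.* Packs hold one week, dispensing is recorded at visits 1 to 4, and each woman has a coordinator for adherence. The 11 weeks may be the nominal test-positive course, which the arithmetic allows at T = 42. Staff can apply the stop rule at visit 4. The quantity dispensed per visit is not stated, so surplus packages cannot be estimated.
- *That no drug comes back.* The caution line can mean that leftovers should not be thrown away, and the end of the trial can mean her last drug visit. The label is also translated from Chinese. Returns remain a visit item. The conflict is on the face of the text and is not proof that returns fail.
- *That section 11 sets a third course length.* Its 3 months is a planning approximation.
- *That all women lost before transfer lack an end of dosing.* The plan's 38% would give 0.38 × 1,466 = 557, but 15% (about 220) are dropouts, who leave under section 4.3. A cancelled cycle might also be handled under 4.3, but that section does not mention cancellation and 12.2 counts it separately from dropout.
- *That compliant test-negative women will be dropped from the per-protocol set.* This needs the 77-day denominator, which the documents do not state.

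What this case does not remove is that the printed instruction omits the pause and the test-dependent end, and that nothing in the plan explains how it fits with 5.4 or with the returns.

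**Conclusion.** The point holds in limited form. One unconditional 11-week period cannot fit two courses that end 21 days apart, and this does not depend on any assumed T. The leftover-drug line conflicts on its face with returns at visits 2 to 5 and weakens the count available to check adherence. Section 5.4 states no end of dosing for cancelled cycles, about 337 of 1,466 women if the plan's 23% is right.

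The effect is on consistency of exposure, drug accountability and per-protocol adherence. Cancelled cycles are excluded from the per-protocol set anyway, so for those women the gap concerns exposure and accountability only. Both arms carry the same label, the primary analysis is by intention to treat, and neither that analysis nor the sample size changes. How far women actually depart from 5.4 cannot be estimated from the documents.

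**What to change.** 1. Reconcile sections 5.4, 5.4.4 and 11 so that the label, or an instruction sheet that goes with it, agrees with the protocol on duration, pause and end of dosing, including when no transfer takes place. The sponsor decides which text stands.
2. Align the leftover-drug line with section 6 by asking women to bring remaining drug and empty packages to those of visits 2 to 5 that they attend.
3. Use the returned-package counts alongside the diary when assessing the 80% rule. The reconciled course would also supply the required dosage that sections 5.4.3 and 12.3 rely on.

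The cost is label text at the next print run, or an interim instruction sheet, and one protocol paragraph. Returns are already recorded, so no new visit or procedure is needed.
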